9.1.12 Sputum Induction

A 12-minute sputum induction using nebulized 3% hypertonic saline will be performed at Visits 3 and 11. All participants will perform baseline spirometry after 4 or more puffs of albuterol administration prior to sputum induction. Peak flow measurements are done

every 2 minutes during the induced sputum collection to assess for excessive bronchoconstriction.

Associated risks include the following:

- Likely (>10%): Salty after taste in the mouth, coughing, or a feeling of needing to swallow
- Less Likely (<5%): Sore throat, shortness of breath, wheezing, chest tightness, light-headedness, nausea, or headache, worsening of lung function
- Rare but serious (<1%): Some patients have had a severe asthma attack or a reaction to the salty water that they breathe in

In an effort to minimize risk to participants, bronchodilator treatment will be available if sputum induction induces a worsening of asthma symptoms. The following safety procedures will be followed for the sputum induction procedure: only participants with a post-bronchodilator FEV1 of > 50% predicted will undergo sputum induction; a physician will be available during the induction; study staff will calculate and record the peak flow and FEV1 value that equals both a 10% and 20% fall in lung function based upon the recorded post-bronchodilator peak flow and FEV1 values; and participants will not be discharged until their FEV1 is within 10% of their post-bronchodilator FEV1.

9.1.13 Point of Care Urine Pregnancy Test

A point of care urine pregnancy test will be obtained from female participants who are of childbearing potential prior to their participation in the study and routinely throughout their participation (see Appendix 1).

9.1.14 CT Imaging of the Thorax

A single inspiratory low dose CT scan of the thorax using a model based iterative reconstruction (MBIR) approach will be taken at the baseline eligibility visit (Visit 2) and following the treatment period over 3 months (Visit 9, 11 and 12).

The risks associated with CT scanning are that of the additional amount of radiation exposure. The additional amount of radiation that each participant will receive as a result of participating in this study will be approximately 5 mSv, which is slightly greater than the yearly natural background of radiation in the US, which is 3 mSv. This amount of radiation may involve a low risk of cancer. A participant should not participate in this study if she is pregnant or breastfeeding.

Additional risks are associated with the uncovering of abnormal findings. There is a risk of possible detection of an abnormality in the lung, which after testing or treatment, is found not to be disease causing. This includes possible misdiagnosis of lung cancer. Such findings may result in unnecessary anxiety for the participant, and increase his or her chance that an outpatient physician may believe that the abnormality is lung cancer and order further testing. This testing could include additional CT scans with additional radiation exposure, other types of scans to determine if the abnormalities are rapidly growing, a needle biopsy (taking a sample of the abnormality with a needle) or a lung biopsy, which requires surgery. Whether these additional studies would be performed would be a decision that the participant would make with his or her regular physician.

In an effort to minimize risk to participants, scans will be read by radiologists that have expertise in interpreting findings of chest CTs. If there are any abnormalities, other than those that are usually found in asthmatic patients, observed by the clinical center radiologists, these would be reported to the principal investigator, who will in turn communicate these findings to the participant. The most likely abnormal result will be the identification of a spot on the lung that might be cancer.

9.1.15 Body Plethysmography

Body plethysmography will be done to determine functional residual capacity (FRC), residual volume (RV), total lung capacity (TLC), and slow vital capacity (SVC) at Visit 3 and 9. Plethysmography will be done with bronchodilation. If bronchodilation procedures are done, participants will follow the medication hold times as described in Section 9.1.2.

In an effort to minimize risk to participants, patients with severe claustrophobia, inability to sit upright in a chamber, inability to perform the panting maneuver, inability to perform maximal inspiratory and expiratory efforts, and known perforated tympanic membrane without a snug-fitting earplug will be excluded from participation in the study.

9.1.16 Measurement of Fractionated Exhaled Nitric Oxide (FeNO)

Fractional exhaled nitric oxide measurement test will be performed at Visits 3-12. Subjects will inhale a full breath of air and then exhale it slowly through a mouthpiece while a device measures the concentration of nitric oxide in the air exhaled. Nitric oxide is a gas normally present in the air exhaled from the lungs.

9.1.17 Adverse Events

Information regarding occurrence of adverse events will be captured throughout the study. Duration (start and stop dates and times), severity/grade, outcome, treatment and relation to study drug will be recorded on the case report form (CRF).

9.2 Clinical Laboratory Measurements

9.2.1 Hematology

Blood will be obtained and sent to the clinical hematology lab for a complete blood count with 5-part differential (CBC-D) (hemoglobin, hematocrit, red blood cell count, white blood cell count, white blood cell differential, and platelet count) and serum IgE for assessment of systemic evidence for infection and inflammation. A CBC-D will be obtained at Visits 3, 9 and 11. A serum IgE will be obtained at Visit 3 only.

Risks associated with hematology include the following risks associated with venipuncture:

- Lightheadedness or nausea while having blood drawn
- Bruising at the site where the needle enters the skin and a remote risk of infection

In an effort to minimize risk to participants, aseptic technique will be used and pressure applied to site to prevent infection/bruising. Participants who have previously identified

that they experience lightheadedness during blood draws will have blood drawn while lying supine on an exam room table.

9.3 Research Laboratory Measurements

9.3.1 Sputum Measurements

Sputum for determination of airway inflammation will be collected and processed. Airway inflammation measurements may include cell count and differential, cytokine gene expression measurements, and rheology.

10 EVALUATIONS BY VISIT

10.1 Visit 1 (Day -14)

1. Review the study with the subject and obtain written informed consent and HIPAA authorization.
2. Assign the subject a unique screening number.
3. Record demographics data.
4. Record medical history, including a history of asthma, diagnosis date, and asthma-related healthcare utilization and exacerbation frequency.
5. Record concomitant medications.
6. Perform a complete physical examination.
7. Perform and record vital signs.
8. Perform and record oximetry.
9. Perform and record urine pregnancy test.
10. Perform and record spirometry.
11. Schedule participant for Visit 2.

10.2 Visit 2 (Day -10)

1. Record changes to concomitant medications.
2. Perform and record vital signs.
3. Perform and record oximetry.
4. Perform and record urine pregnancy test.
5. Perform and record spirometry.
6. Perform and record maximum bronchodilator spirometry.
7. Obtain a CT scan of the thorax.
8. Schedule participant for Visit 3 if CT mucus plug score is equal to or greater than 5.

10.3 Visit 2b (Day -7) *Optional***

1. Record changes to concomitant medications.
2. Perform and record vital signs.
3. Perform and record oximetry.
4. Perform and record urine pregnancy test.
5. Perform and record spirometry.
6. Perform methacholine challenge testing.
7. Obtain a CT scan of the thorax.
8. Schedule participant for Visit 3 if CT mucus plug score is equal to or greater than 5.

10.4 Visit 3 (Day -5)

1. Record changes to concomitant medications.
2. Perform and record vital signs.
3. Perform and record oximetry.
4. Perform and record urine pregnancy test.
5. Perform and record fractional exhaled nitric oxide (FeNO) measurement.
6. Perform and record spirometry.
7. Collect blood sample for clinical laboratory tests.
8. Perform and record plethysmography with bronchodilation.
9. Collect induced sputum.
10. Schedule participant for Visit 4.

10.5 Visit 4 (Day 1)

1. Record changes to concomitant medications.
2. Perform and record vital signs.
3. Perform and record oximetry.
4. Perform and record fractional exhaled nitric oxide (FeNO) measurement.
5. Perform and record spirometry.
6. Perform and record 3 peak flow AM measurements before first treatment of the day.
7. Perform and record post-bronchodilator reversibility.
8. Admit patient to medical-surgical floor.
9. Administer study drug treatment three times over the course of the day, spaced every 4-6 hours. Peak flow measurements should be taken before and after each treatment.
10. Perform and record 3 peak flow PM measurements after all treatments have been completed.

10.6 Visit 5 (Day 2)

1. Perform and record fractional exhaled nitric oxide (FeNO) measurement.
2. Perform and record spirometry.
3. Perform and record 3 peak flow AM measurements before first treatment of the day.
4. Administer study drug treatment four times over the course of the day, spaced every 4-6 hours. Perform peak flow measurements before and after each treatment.
5. Perform and record 3 peak flow PM measurements after all treatments have been completed.

10.7 Visit 6 (Day 3)

1. Perform and record fractional exhaled nitric oxide (FeNO) measurement.
2. Perform and record spirometry.
3. Perform and record 3 peak flow AM measurements before first treatment of the day.
4. Administer study drug treatment four times over the course of the day, spaced every 4-6 hours. Perform peak flow measurements before and after each treatment.
5. Perform and record 3 peak flow PM measurements after all treatments have been completed.

10.8 Visit 7 (Day 4)

1. Perform and record fractional exhaled nitric oxide (FeNO) measurement.
2. Perform and record spirometry.
3. Perform and record 3 peak flow AM measurements before first treatment of the day.
4. Administer study drug treatment four times over the course of the day, spaced every 4-6 hours. Perform peak flow measurements before and after each treatment.
5. Perform and record 3 peak flow PM measurements after all treatments have been completed.

10.9 Visit 8 (Day 5)

1. Perform and record fractional exhaled nitric oxide (FeNO) measurement.
2. Perform and record spirometry.
3. Perform and record 3 peak flow AM measurements before first treatment of the day.
4. Administer study drug treatment four times over the course of the day, spaced every 4-6 hours. Perform peak flow measurements before and after each treatment.
5. Perform and record 3 peak flow PM measurements after all treatments have been completed.

10.10 Visit 9 (Day 6)

1. Discharge patient from medical-surgical floor.
2. Perform and record vital signs.
3. Perform and record oximetry.
4. Perform abbreviated physical exam.
5. Perform and record urine pregnancy test.
6. Perform and record fractional exhaled nitric oxide (FeNO) measurement.
7. Perform and record spirometry.
8. Perform and record post-bronchodilator reversibility.
9. Perform and record plethysmography with bronchodilation.
10. Obtain a CT scan of the thorax.
11. Collect blood sample for clinical laboratory tests

10.11 Visit 10 (Day 13)

1. Perform and record vital signs.
2. Perform and record oximetry.
3. Perform and record fractional exhaled nitric oxide (FeNO) measurement.
4. Perform and record spirometry.
5. Perform and record post-bronchodilator reversibility.

10.12 Visit 11 (Day 48)

1. Perform and record vital signs.
2. Perform and record oximetry.
3. Perform and record urine pregnancy test.
4. Perform and record fractional exhaled nitric oxide (FeNO) measurement.

5. Perform and record spirometry.
6. Perform and record post-bronchodilator reversibility.
7. Obtain a CT scan of the thorax.
8. Collect blood sample for clinical laboratory tests.
9. Collect induced sputum.

10.13 Visit 12 (Day 91)

1. Perform and record vital signs.
2. Perform and record oximetry.
3. Perform and record urine pregnancy test.
4. Perform and record fractional exhaled nitric oxide (FeNO) measurement.
5. Perform and record spirometry.
6. Perform and record post-bronchodilator reversibility.
7. Obtain a CT scan of the thorax.

10.14 Early Withdrawal Visit (Before end of Visit 3)

1. Record any adverse experiences.
2. Record changes to concomitant medications.
3. Perform and record vital signs.
4. Perform and record oximetry.
5. Perform abbreviated physical examination.
6. Perform and record spirometry.

10.15 Late Withdrawal Visit (After Visit 3 Completion)

1. Record any adverse experiences.
2. Record changes to concomitant medications.
3. Perform and record vital signs.
4. Perform and record oximetry.
5. Perform abbreviated physical examination.
6. Perform and record fractional exhaled nitric oxide (FeNO) measurement.
7. Perform and record spirometry.
8. Perform and record post-bronchodilator reversibility.
9. Collect blood sample for clinical laboratory tests.
10. Obtain a CT scan of the thorax.

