12 DISCONTINUATION AND REPLACEMENT OF SUBJECTS

12.1 Early Discontinuation of Study Drug

A subject may be discontinued from study treatment at any time if the subject, the investigator, or the Sponsor feels that it is not in the subject's best interest to continue. The following is a list of possible reasons for study treatment discontinuation:

Subject withdrawal of consent

Subject is not compliant with study procedures

Adverse event that in the opinion of the investigator would be in the best interest of the subject to discontinue study treatment

- Protocol violation requiring discontinuation of study treatment
- Lost to follow-up
- Sponsor request for early termination of study
- Positive pregnancy test (females)

If a subject is withdrawn from treatment due to an adverse event, the subject will be followed and treated by the Investigator until the abnormal parameter or symptom has resolved or stabilized.

All subjects who discontinue study treatment should come in for an early discontinuation visit as soon as possible and then should be encouraged to complete all remaining scheduled visits and procedures.

All subjects are free to withdraw from participation at any time, for any reason, specified or unspecified, and without prejudice.

Reasonable attempts will be made by the investigator to provide a reason for subject withdrawals. The reason for the subject's withdrawal from the study will be specified in the subject's source documents. Refer to Section 10 for early termination procedures.

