[name], MSC
Clinical Research Protocol
INPATIENT CLINICAL TRIAL OF NAC IN ASTHMA (ICON)

Protocol Number:	17-24231
NCT Number	NCT03581084
Investigational Product:	n-acetylcysteine
Development Phase:	4
Sponsor:	[name], MSc [name]
Funding Organization:	NIH
Principal Investigator:	Name: [name], MSc [contact] [contact] E-mail: [contact]

STATISTICAL ANALYSIS PLAN

Our overarching method (experimental approach) is to test the efficacy of inhaled NAC delivered for 5 days to asthma patients who have baseline evidence of mucus plugs on CT lung scans. We will assess if the NAC treatment causes the mucus plugs to go away by the end of the treatment period and we will assess for reappearance of mucus plugs at 6 weeks and 3 months time. We will also examine whether any NAC associated decrease in mucus plugs is associated with improvement in FEV1. A primary analysis will be paired T-test analysis of the change in CT mucus plug score and in FEV1 from baseline to end treatment. Secondary analyses will look at the 6 week and 3 month time points.

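### The Late Withdrawal Visit is triggered by completing Visit 3 rather than by the first dose, so a participant who leaves undosed is sent for a second thorax CT that no planned analysis can use

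*Protocol*

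**What the plan says.** Section 10 of the protocol splits leavers into two groups at Visit 3. Section 10.14 (before the end of Visit 3) asks for adverse events, medication changes, vital signs, oximetry, a short physical examination and spirometry. Section 10.15, "Late Withdrawal Visit (After Visit 3 Completion", adds FeNO, post-bronchodilator reversibility, a blood sample and, as its last item, "Obtain a CT scan of the thorax". It attaches no condition about dosing or about the date of the last scan.

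Visit 3 is headed "10.4 Visit 3 (Day -5". Dosing begins at Visit 4 (Day 1), where the instruction is "Administer study drug treatment three times over the course of the day".

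The SAP plans a "paired T-test analysis of the change in CT mucus plug score and in FEV1 from baseline to end treatment", with secondary analyses at 6 weeks and 3 months. Protocol 15.3 adds the relation between FEV1 change and CT score change. Section 15.1 defines only a Safety Population, which requires at least one dose. Section 12.3 replaces both those who withdraw from treatment and those who withdraw from the study.

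Under section 12.1, participants who stop study drug "should come in for an early discontinuation visit as soon as possible and then should be encouraged to complete all remaining scheduled visits and procedures", and it points to section 10 for the procedures. Section 12.2 repeats the early discontinuation visit for those who stop before Visit 8. For withdrawals after Visit 8 and before Visit 11 it substitutes the procedures of the next scheduled visit.

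Section 9.1.14 and Appendix 1 list CT at Visits 2, 9, 11 and 12. On dose, 9.1.14 says: "The additional amount of radiation that each participant will receive as a result of participating in this study will be approximately 5 mSv".

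**The concern.** A withdrawal CT is useful when it captures an outcome after exposure to the drug. The 10.15 trigger falls before any exposure. An undosed leaver would take on radiation, and the risk of incidental findings that 9.1.14 itself describes, without contributing to any planned result. The protocol gives no other purpose for the scan.

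A lesser concern is participants who stop NAC early but remain in follow-up. If the visit required by 12.1 is the one in 10.15, they have a CT there and another at Visit 9 a few days later. The first of these appears in neither 9.1.14 nor Appendix 1, and the SAP does not link end of treatment to a visit.

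**Working it through.** **The plan's own figures.** The sample size of 30 reproduces closely: (19 × (1.960 + 0.842) / 10)² = 28.3, so 29 by the normal approximation. The noncentral t distribution gives 79.6% power at 30. Nothing below depends on it. The 5 mSv figure cannot be reproduced, because no dose per scan is given.

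**Undosed leavers: the window.** From Visit 3 (Day -5) to Day 1 is 5 days, counting no Day 0. With the ±2 days that Appendix 1 allows at Visit 3, it is 3 to 7 days. Anyone leaving in this window meets the 10.15 condition and not the 10.14 condition.

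**Undosed leavers: the gap between scans.** The screening CT is at Visit 2, nominally Day -10. A withdrawal CT between Day -5 and Day 1 comes 5 to 10 days later. It comes later still if the visit takes time to arrange, since 10.15 sets no time limit; hence roughly one to two weeks.

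**Undosed leavers: can the scan be analysed?**
- Baseline to end of treatment: there was no treatment period.
- 6 weeks and 3 months: there is no treatment to count from.
- CT change against FEV1 change: there is no treatment response to relate.
- Safety Population: not met, as no dose was received.
- Replacement: 12.3 applies.

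The protocol defines no efficacy population, so exclusion of undosed participants is implied by these analyses rather than written down.

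**Early stoppers who stay on, if the 12.1 visit is 10.15.** Stopping on Day 1, 2, 3, 4 or 5 with a same-day visit puts that CT 5, 4, 3, 2 or 1 days before the Visit 9 CT on Day 6. A participant who completes follow-up then has 4 + 1 = 5 scans.

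**Exposure, by assumption.**

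| Assumption about the stated 5 mSv | Per scan | Five scans | Excess over 5 mSv |
|---|---|---|---|
| Covers the four listed scans equally | 5/4 = 1.25 mSv | 6.25 mSv | 1.25 mSv |
| Already allows for five equal scans | 5/5 = 1.0 mSv | 5 mSv | none |

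Under the same two assumptions, the undosed leaver's unusable scan is 1.0 to 1.25 mSv. That person's two-scan total (2.0 to 2.5 mSv) stays below 5 mSv. The objection there is lack of purpose, not an exceeded figure.

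These counts leave out optional Visit 2b (10.3), which also lists a thorax CT but is absent from 9.1.14 and Appendix 1. If that scan is additional to Visit 2, each count rises by one.

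**The case against.** The best defence on the main point is scale. The window is a few days, participants may leave freely and need not accept a scan, and perhaps nobody will be affected. That limits the importance but does not give the scan a use.

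The defence is stronger on early stoppers. Section 12 separates stopping the drug (12.1) from leaving the study (12.2), and 10.15 is labelled a withdrawal visit. Someone who stops NAC and stays on has not withdrawn. Matching the two visits is an inference. It is plausible, because 12.1 refers to section 10 and 10.15 is the only withdrawal visit there that fits a dosed participant, but the text does not say so.

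A reader might also infer that early stoppers leave two competing end-of-treatment scores, to be chosen between once both are known. The documents do not support that. Section 9.1.14 and Appendix 1 place the first post-treatment CT at Visit 9. The SAP's 6-week point fits that anchor, since Visit 11 on Day 48 is 48 - 6 = 42 days after Visit 9. A withdrawal CT is in neither schedule. Section 8.2 unblinds treatment, but nothing describes how or when CT scores are read. What stands is that the SAP lacks a sentence naming the visit.

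Nor can each early stopper be counted as one of 30 pairs. Section 12.3 replaces them without saying whether their data stay in, so their share could be zero, or could be taken over a denominator above 30.

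**Conclusion.** The main point holds on the text: 10.15 sends undosed leavers for a thorax CT that no listed analysis can use. It is a minor fault affecting few participants, with no effect on the sample size or on analysable data.

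The secondary point is conditional. A duplicate CT for early stoppers arises only if the visit in 12.1 is 10.15 and the participant also attends Visit 9. It would be tempting to report their exposure as 25% above the stated figure, but that holds only if 5 mSv covers exactly four equal scans. The supportable range is an excess of none to about 1.25 mSv.

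Separately, 10.15 and 12.2 give different instructions after Visit 8. For example, someone leaving between Visits 9 and 10 has a CT under 10.15 but none under 12.2, because Visit 10 has no CT. These passages must be reconciled.

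**What to change.** 1. In 10.15, make the trigger receipt of the first dose of study drug instead of completion of Visit 3, and extend 10.14 to everyone who leaves undosed. This also drops FeNO, reversibility and blood sampling for undosed leavers. None of these would inform a treatment comparison in someone never treated.
2. State which section 10 visit is meant by the early discontinuation visit in 12.1 and 12.2, and reconcile 10.15 with the 12.2 rule that applies after Visit 8. If a withdrawal CT is kept for dosed participants, list it in 9.1.14 and say whether the 5 mSv includes it.
3. Add a sentence to the SAP that Visit 9 (Day 6) supplies the end-of-treatment CT score and FEV1. Whether replaced participants' data are analysed is a separate gap under 12.3, which that sentence does not settle.

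The cost is a short amendment and one SAP sentence, with fewer scans and no loss of analysable data from item 1. Skipping the withdrawal CT for early stoppers expected at Visit 9 would remove the duplicate, but anyone who then missed Visit 9 would have no CT at the end of treatment. That is a trade-off for the sponsor to decide, and item 1 does not depend on it.
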